HIPAA	Health Insurance Portability and Accountability Act of 1996
ICF	Informed consent form
ICH	International Conference on Harmonization
ACMJE	American Committee of Medical Journal Editors
IFU	Instructions for Use
IRB	Institutional review board
IR	Interventional Radiologist/Radiology
Kg	Kilogram
LDCT	low-dose computed tomography
mcg	Microgram (µg)
mg	Milligram
mL	Milliliter
MedDRA	Medical Dictionary for Regulatory Activities
MIV	Minimally invasive
mm	Millimeter
NCCN	National Comprehensive Cancer Network
PI	Principal Investigator
PPN	Peripheral pulmonary nodules
SAE	Serious adverse event
SD	Standard Deviation
SOP	Standard Operating Procedures
SPiN or SPiN System	SPiN Thoracic Navigation System™
US	United States of America
VATS	Video assisted thoracoscopic surgery
VERAN	Veran Medical Technologies, Inc.

STUDY SYNOPSIS

SPONSOR	Veran Medical Technologies, Inc.
PRODUCT	SPiN Thoracic Navigation System™, including Localization Needles, SPiN Perc™ Kit, other accessories per investigator discretion
TITLE	Intraoperative, Percutaneous Localization of Peripheral Pulmonary Nodules for Resection: a Prospective, Open-Label , Multi-Center Registry Study of Thoracic Surgery Outcomes .
STUDY NUMBER	VMT-01-003
STUDY PHASE	Post-marketing Registry/IV
LOCATION	This trial will be conducted at approximately 5 sites across the US.
NUMBER OF SUBJECTS	The study aims to report 70-100 subjects. Each site is expected to enroll a minimum of 6 subjects.
OBJECTIVES	
The registry is aimed developing a high-quality set of data regarding intraoperative percutaneous localization of peripheral pulmonary nodules (PPNs), and then identifying and promulgating efficient, evidence-based best practices for this technique. The resection procedure itself is standard of care and follows the investigator's standard protocol.
 
Successful localization of PPNs is a challenge involving multiple factors, beginning with the subjects' health, lung function and also factors specific to the nodule including location within the lung, size, distance from the lung surface, whether solid or ground glass and proximity to a fissure. Hard to see or palpate nodules are currently localized with dye and/or hook wires or fiducials, either endoscopically or percutaneously. Successful, large, prospective studies have not been reported using modern electro-magnetic navigation (EMN)-guided percutaneous intraoperative localization, and different techniques (dye vs. fiducial vs. hook wire etc.) have not been evaluated. It is for these reasons that the different localization techniques used with EMN-guided percutaneous localization will be collected for patients having a suspicious nodule and who undergo percutaneous intra-operative localization and immediate resection.
 
This registry aims to record the localization techniques used by thoracic surgeons and IP/surgical teams to identify PPNs using the SPiN Thoracic Navigation System™ in the hands of trained physicians. The objectives of this study will be to accomplish the

	primary and secondary objectives listed below, and to observe localization in a real-world context of pulmonary resection.
PRIMARY OBJECTIVE	Successful percutaneous localization of PPN. This is defined as the percentage of subjects in whom the nodule is successfully localized and removed in the first resected specimen. A pathological specimen with clear margins will count as a successful localization.
SAFETY OBJECTIVES	
1. Report the incidence of device-related adverse events that occur during the localization procedure.
SECONDARY OBJECTIVES	
1. Report localization methods and techniques – dye and materials used, volume of dye (methylene blue, ICG etc.), other materials such as microcoils, hook wires etc. Details regarding these techniques will be collected.2. Collect data on intraoperative percutaneous localization time and duration of total surgical procedure.3. Record nodule characteristics, including location in the lobe, distance from pleura, distance from surface of skin to target, morphological appearance, solid vs ground glass etc.4. Record weight of excised tissue and margin.5. Report type of surgical resection performed (segmentectomy or wedge) and resection technique (VATS, RATS, thoracotomy).
STUDY DESIGN	
The registry is designed to collect data about subjects who fall within the current practice, and to better understand effective intraoperative localization techniques used by thoracic surgeons to localize small, suspicious lesions just prior to surgery. The SPiN System and tools are a medical device that is 510(k) exempt under 21 CFR 812.2(c)(2), which applies to the investigation. The 510(k) product is being used in accordance with the product labeling (Appendix A).
 
This is a prospective, multicenter, open-label, single arm registry to record the safety, efficacy, and methodology of percutaneous, intraoperative localization of PPNs immediately prior to lung resection. As such, it is a technical procedure registry designed to better understand the various factors which affect percutaneous localization.
 
Thoracic surgeons of varying levels of experience in EMN-guided percutaneous localization will be trained on localization tools and techniques using the SPiN System – with didactic peer-to-peer presentations, followed by device training and hands-on experience with phantoms and/or cadavers.

	
The study will enroll between 70 and 100 subjects who fall within current clinical practices to have their PPNs removed at approximately 5 geographically diverse sites across the US. These subjects will undergo intraoperative, EMN-aided percutaneous nodule localization and subsequent resection as part of their normal care. Safety data (adverse and severe adverse events) regarding these subjects will be collected for the localization procedure.
 
All surgical and post-surgical treatment decisions and clinical assessments will be at the discretion of the subject's thoracic surgeon. Eligible subjects from participating sites will be enrolled following identification of a qualifying nodule, and meeting inclusion/exclusion criteria and completing informed consent.
 
Data Collection
 
Registry data will be collected before, during, and after the procedure from the subject's medical records by site personnel. Based on current clinical practice, it is anticipated that subjects will be seen following nodule identification and workup to determine the treatment plan and preparation for surgery (baseline visit). The size and location of the nodule, demographic data and data about smoking history will be collected. Comorbidities will be collected from medical history, and the subject's lung function test results collected.
 
The subject will return to the site for surgery. A non-contrast chest CT scan is recommended within 24 hours/same day as surgery, as a clinically indicated procedural planning tool (Appendix D – Veran CT scan). Otherwise, a non-contrast chest CT scan within the past 15 days is adequate. Subjects are typically given general anesthesia for surgery. The localization technique and material used will be recorded, including volume and type of dye, which needle used, and any other fiducial markers (e.g. microcoil). Localization procedure-related adverse events and device-related adverse events will be recorded. The type and technique of resection performed will be collected (VATS, RATS, thoracotomy, etc.). Subjects recover in hospital and are discharged per standard of care. Any localization-related adverse events will be reported, however the overall lung surgery procedure itself is not being studied (approved indication). Subjects will typically return to the clinic a few times to be seen for scheduled post-operative visits to monitor recovery.
 
A secure, site portal that is 21 CFR part 11 compliant is used for the electronic data entry and reporting at each site, which includes appropriate firewalls between sites and users to protect subject

--	---

	PHI and privacy. All data collected into the study database will be de-identified at the site level.
STUDY PROCEDURES	
Subjects are treated for lung resection according to the treatment devised by their clinician.
 
Part of the technical procedure registry trains thoracic surgeons on the various available tools and techniques in intraoperative localization, using both didactic review, best practices, case review, and a cadaver lab.
 
The following represents the typical standard of care for this procedure. The registry study is nested within the standard lung resection operation, and study procedures on data collection are described within the context of these procedures for clarity of identification:
 
Following nodule identification and referral, subjects are typically evaluated per the subject inclusion/exclusion criteria. Review of the subject's CT/PET scan demonstrate a PPN that is between 0.4 cm and 3.2 cm in its longest dimension. All subjects will sign and date an Informed Consent Form (ICF) before enrollment (Baseline Visit).
 
Subjects will undergo a chest CT scan on the day of surgery, verifying the longest dimension of the nodule (data collected). The subject is put under general anesthesia. The SPiN Percutaneous nodule localization procedure is performed intraoperatively, using dye and/or other localization techniques. A surgical resection (wedge, segmentectomy etc.) will follow, according to PI's judgment. Subjects are generally hospitalized between 2-5 days following this procedure and discharged. Following discharge, subjects typically follow a schedule of multiple clinic visits, as determined by their healthcare team. Subject participation in the localization registry will end following hospital discharge.

ESTIMATED DURATION OF STUDY	The Registry is anticipated to take 24 months to complete.

STUDY POPULATION	
The target subject population includes adult subjects (18 years-85 years), with PPNs. In the judgment of the thoracic surgeon, localization for resection is warranted via a percutaneous localization approach. The establishment of malignancy is not necessary for PPN removal.
 
Data will be collected from study subjects having a PPN between 0.4 cm and 3.2 cm in greatest dimension, that are accessible to percutaneous localization, who consent to and undergo intraoperative dye/wire localization procedure followed by surgical lung resection.

-------------------------	--

DIAGNOSIS AND MAIN CRITERIA FOR INCLUSION	
Subjects will be eligible to enroll into the registry if they have given their informed consent and also meet the following criteria:
 
Inclusion criteria:
 
• Subject's physician and/or thoracic surgeon have deemed/has deemed that the surgical removal of the PPN is appropriate.• A clinical decision has been made to use the SPiN Thoracic Navigation System™.• Subject is at least 18 years of age at time of study entry.• Subject is able to read, understand, and voluntarily sign the IRB-approved informed consent document prior to the performance of any study-specific procedures. IRB-approved translation may be used if indicated. Reasonable accommodation of visually impaired subjects will be allowed.• Subject is able to tolerate general anesthesia.• Subject has a target nodule between 0.4 cm and 3.2 cm in greatest dimension;• The target nodule is in a location that is accessible for percutaneous localization in the judgement of the surgeon. 
Exclusion criteria:
 
• Subjects with any other concomitant treatment or medical condition that, in the opinion of the clinician, would render peripheral nodule resection more hazardous than beneficial.• Subject is pregnant.• Pulmonary nodule is greater than 3.2 cm.• Subjects with significant coagulopathy having INR >2.0 or PTT > 2x normal.• Subject is unable to tolerate general anesthesia• Obese subject, impacting percutaneous access (BMI >50)
TEST PRODUCT AND MODE OF ADMINISTRATION	
Localization of nodules will be completed with the SPiN Thoracic Navigation System™, and the corresponding tools that allow for percutaneous access. These include the SPiN Perc™ Kit and the 1 cm and 2 cm Localization Needles. Please refer to protocol section 5, and also the IFU and product information (Appendix A). Investigators are trained in the use of the tools and the system.

REFERENCE THERAPY	Historical data as available.
DURATION OF SUBJECT INVOLVEMENT	Duration of treatment studied during the registry will be up to approximately 6 weeks per subject, including screening and baseline visits, surgery, and hospital visit.
SAFETY ASSESSMENTS	Localization-related events will be collected.
STATISTICAL ANALYSIS	
Statistical Considerations
 
This is a registry study where no formal hypothesis is being tested. Data collected during the study will be summarized using descriptive statistics and graphical displays. Generally, demographic and other descriptive characteristics will be described as counts and percentages for categorical variables and as measures of central tendency (mean, median, standard deviation [SD], and range) for continuous variables. Ninety five percent (95%) confidence intervals will be presented for key variables and measures of effect. In some cases, data may be summarized by demographic, response, or treatment subgroups (for example by age, sex, nodule size, smoking history and post-surgical smoking pack years, pulmonary function tests, etc.). No adjustments will be made for multiple comparisons. All localization-related adverse events will be listed and summarized.
 
Interim and Final Analyses
 
Data collected during the study, which is open-label and non-randomized, will be analyzed and reported periodically by an executive steering committee comprised of thoracic surgeons. When the study is completed, a final analysis will be performed and reported.

DATE OF ORIGINAL PROTOCOL	June 11, 2019
DATE OF AMENDMENT	November 2, 2020

1. STATEMENT OF COMPLIANCE

This human subject study will comply with all applicable federal, state, and local laws and regulations, including generally accepted standards of good clinical practice as adopted by current Food and Drug Administration (“FDA”) regulations and statutes. Participating study sites shall only allow individuals who are appropriately trained and qualified to assist in the conduct of the Study.

2. BACKGROUND

Within the past several years, small and suspicious pulmonary nodules have raised a difficult issue for internal medicine physicians, pulmonologists, interventional radiologists, and cardiothoracic surgeons. Depending upon the size, location, and type of nodule, they can be challenging to precisely locate and remove. The nodules, including those studied here between 0.4 cm and 3.2 cm along their longest axis, are often found incidentally usually on Computed Tomography (CT) scans and sometimes on chest X-rays. In studies of incidentally detected nodules, the prevalence of malignancy ranges from 2-82% (Wahidi *et al*, 2007).

There is an opportunity to develop efficient tools and procedures to more precisely target these PPNs. Depending on the patient, this targeted approach may also offer the best opportunity to preserve as much remaining lung function as possible in cases where subjects have respiratory comorbidities. Thus, developing and describing a streamlined, reproducible and accurate approach to nodule localization is a method that holds promise for thoracic surgeons.

Current recommendations from the American College of Chest Physicians (ACCP) evidence-based guidelines for the management of pulmonary nodules begin with examination of the nodule, and an estimation of the clinical probability that the nodule is malignant and evaluation of surgical risk. For subjects with a high probability of cancer (>60%), diagnosis by biopsy and resection are recommended. More than 40% of lung targets are not accessible by conventional bronchoscopy due to their location, with contributing factors including the small diameter of the airways, lack of an airway leading to a nodule and maneuverability difficulties (Rivera *et al*, 2003; Alberts and Colice, 2003).

The ability to identify and to obtain diagnostic tissue from PPNs has been evaluated in clinical trials using techniques such as diagnostic bronchoscopy alone, and then in comparison, with EMN-guided bronchoscopy and r-EBUS (Ost *et al*, 2016). A large, multicenter registry-based clinical effectiveness study (AQuIRE Registry) (*ibid..*). The AQuIRE registry had a primary objective to measure and identify the determinants of diagnostic yield for bronchoscopy in patients with peripheral lung lesions. Secondary outcomes included diagnostic yield of different sampling techniques, complications, and practice pattern variations. Subjects were enrolled at 15 centers having 22 study physicians between 2009-2014, and the registry was funded by the CHEST organization.

Ost *et al.* reported unexpectedly low diagnostic yields for electromagnetic navigation. Regarding the low EMN rate, one AQuIRE principal investigator (PI) noted “more than 98% of the EMN cases were performed with a single system (Medtronic, Minneapolis, MN) that lacks additional capabilities, including TTNA under EMN guidance. Since the completion of enrollment in the AQuIRE study, newer EMN technologies have been developed and now allow for a navigational transthoracic approach.”

- The AQuIRE registry had a primary objective to measure and identify the determinants of diagnostic yield for bronchoscopy in patients with peripheral lung lesions. Secondary outcomes included diagnostic yield of different sampling techniques, complications, and practice pattern variations.
- The AQuIRE registry reported poor diagnostic yields for multiple modalities
 - Bronchoscopic alone: 53.7%
 - r-EBUS when used alone: 57%
 - EMN Yield when used alone was 38.5% (98% of cases were SuperDimension technology)

Of these, 312 subjects in the trial underwent transbronchial biopsy. Using bronchoscopy alone, the diagnostic yield was reported as 63.7%. In earlier work, the average diagnostic yield for peripheral lung lesion biopsy performed with conventional flexible bronchoscopy was reported to be 69% for peripheral lesions greater than 20 mm and 33% for peripheral lesions less than 20 mm, (Mazzone *et al*, 2002; Rivera *et al*, 2003; Schrieber and McCrory, 2003).

Results from studies involving procedural guidance technologies such as electromagnetic navigation (EMN) and radial endobronchial ultrasound (radial EBUS) have also been reported (Ost *et al.*, 2016). Diagnostic yield was reported at 57% with r-EBUS alone, 47.1% with EMN combined with r-EBUS. In another recent study published in the New England Journal of Medicine, a total of 639 subjects underwent bronchoscopy for suspected lung cancer and of those bronchoscopic examinations, 43% were nondiagnostic, including in 25% (120 of 487 subjects) in whom lung cancer was ultimately diagnosed.⁹ As a result of published yields showing an unacceptable yield for peripheral bronchoscopy, ACCP guidelines recommends that nodules without a CT-bronchus sign should be pursued with EMB-TTNA (Rivera *et al*, 2013).

Veran’s novel electromagnetic system (EMN) bronchoscope and toolkit use the EMN field with several “Tip Tracked” nodule localization instruments, and a bronchoscope to generate three dimensional maps of lung tissue and airways. The “Tip Tracked” instruments display their location during the procedures. The generated maps provide continuous, “real-time” navigational tracking, identifying an efficient path to localizing nodules only a few millimeters along their longest axis. Providing the operator with assisted lung nodule localization and navigation have improved diagnostic yields. The system uses the recent chest CT scan image and combines it with the bronchoscope to align the subject’s body with the CT images. This allows for the construction of 3-D virtual bronchoscopy images and the ability to navigate throughout the lung with a CT-correlated roadmap. As the operator steers the bronchoscope, a real time distance to target is generated, that can be used for the precise localization of small lesions.

Localization of the peripheral nodules in the outer lung regions can be accomplished intraoperatively, just prior to surgical resection, with the same surgical staff who are performing the operation. This eliminates an additional step for the thoracic surgeon (or other oncology team member) and also for the subject, namely identifying and coordinating with persons from other departments who may typically place fiducial, hookwire, and microcoils as separate procedures, involving additional resources. In addition, the migration of these markers, and the need to verify their placement with an additional CT or other scan prior to surgery, are potentially steps that may be able to be streamlined. The overarching objective is to keep this localization and resection procedure within the hands of the principal investigator, and to quantify the percentage of subjects in whom the nodule is removed in the first resected specimen, procedure time, and nodule characteristics and procedure details and techniques.

3. RATIONALE

Veran Medical Technologies, Inc. is seeking to characterize the efficient localization and successful removal of PPNs aided by the technique of percutaneous localization within the operating room. This falls within the current practice for these subjects. However, the characterization and comparison of various localization techniques has not been reported prospectively in a large, multicenter approach.

To realize this opportunity, further localization methodologies must be developed. Percutaneous nodule localization involves various factors. Nodular size and location (near the pleura) can both introduce challenges for unequivocal localization and complete removal. PPNs can be difficult to locate and access in order to mark them. It can be difficult to find the marked nodules, depending upon the location and how well the localization technique worked during the resection surgery. This registry will collect data regarding different techniques used by thoracic surgeons using a choice of localization materials (dye, hookwire etc.) and with electromagnetic navigation guidance using a transthoracic approach. Evidence from a multicenter, prospective registry trial on localization procedures will allow us to understand the best practices in the localization of PPNs that also minimizes risks in subjects who are typically older, have comorbid lung disease, poor pre-surgical lung function and may have early stage lung cancer.

[figure not shown]
Further, the study will allow us to describe the use of VERAN SPiN Thoracic Navigation System™ and percutaneous lung localization tools in a real-world thoracic surgery practice, including duration of localization procedure, duration of the resection procedure, and other data elements.

TABLE 1 – SCHEDULE OF EVENTS

Procedures/Data Collection	Baseline Visit	Day 0 Surgery Localization Procedure
Nodule is correct size and suitable for percutaneous localization during surgical resection procedure.	X	X
Subject meets Inclusion/Exclusion criteria review.	X	
Subject is able and willing, and signs consent form.	X	
Pregnancy test- urine or serum, for females of child-bearing potential.	X	X
Socio-demographic information.	X	
Pulmonary function test results	X	
Brief Medical History, including previous cancer diagnoses, smoking, and treatment history.	X	
Nodule hx, dx, characteristics if known.	X	
Recent (0-15 days) CT scan available, or schedule CT scan to be used on day of surgery, prior to procedure.	X	X
AEs and SAEs.	X	X
Reason for discontinuation in study or withdrawal if applicable.		

All data generated from this study will be the exclusive property of Veran Medical Technologies, to be used with expressed permission only.

TABLE 2 – Registry Study Flow¹

¹ Surgery: Day 0 is when the subject has the CT scan, procedure of PPN Localization and also lung resection.

² The number of days a subject is hospitalized is per investigator practice. It is recorded as a data element.

³ The actual day of discharge is per investigator's practice. It is recorded as a data element.

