4. OBJECTIVES

The registry is aimed at developing a high-quality set of data regarding the percutaneous localization of PPNs. The localization registry itself is nested within the subjects' lung resection operation. Analyzing and promulgating evidence-based best practices for lung nodule localization will allow surgeons to identify technical solutions and reproducible methods.

This registry will record procedural data for trained thoracic surgeons using the SPiN Thoracic Navigation System™ and tools. Diagnostic yield will measure successful localization of the lesion in the resected specimen. Localization-related safety events will be collected.

4.1 Primary Objective:

Successful percutaneous localization of PPN.

To evaluate the accuracy of percutaneous nodule localization using the SPiN Thoracic Navigation System™ and its accessories, Veran will record the percentage of successful resections that result in the complete removal of the patient's nodule, with a negative margin. The diagnostic yield is calculated as the percentage of patients who have intra-operative localizations resulting in complete removal of nodule, divided by the total number of evaluable subjects. Evaluable subjects are those who complete the localization procedure.

Primary Objective: Successful percutaneous localization of PPN.

This is defined as the percentage of subjects in whom the nodule is successfully localized and removed in the first resected specimen. A pathological specimen with clear margins will count as a successful localization.

4.2 Safety Objective:

Collect safety data for localization procedure.

4.3 Secondary Objectives:

Secondary Objectives: Use as per synopsis – including margin.

- 4.3.1 Report localization methods and techniques – dye and materials used, volume of dye (methylene blue, ICG etc.), other materials such as microcoils, hook wires etc. Details regarding these techniques will be collected.
- 4.3.2 Collect data on intraoperative percutaneous localization time and duration of total surgical procedure.
- 4.3.3 Record nodule characteristics, including location in the lobe, distance from pleura, distance from surface of skin to target, morphological appearance, solid vs. ground glass etc.
- 4.3.4 Record weight of excised tissue and margin.
- 4.3.5 Report type of surgical resection performed (segmentectomy or wedge) and resection technique (VATS, RATS, thoracotomy).

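### Does the aim of finding best practices need a planned, confounder-adjusted comparison of localization techniques?

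*Combined protocol and SAP*

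**What the plan says.** The ambitious wording appears in three places. The synopsis objectives include "identifying and promulgating efficient, evidence-based best practices for this technique". Section 4 opens with "Analyzing and promulgating evidence-based best practices for lung nodule localization". Section 3 is milder: evidence from a multicenter "registry trial on localization procedures will allow us to understand the best practices in the localization of PPNs", with no mention of promulgating or of evidence-based practice.

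Two statements name technique comparison as the gap. The synopsis notes that "different techniques (dye vs. fiducial vs. hook wire etc.) have not been evaluated", and section 3 says that "characterization and comparison of various localization techniques has not been reported prospectively in a large, multicenter approach".

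The commitments are narrower. The primary objective (4.1, 9.2) is one percentage: subjects whose nodule is localized and removed in the first specimen. Objective 4.3.1 reports the methods and materials used, and 4.3.3 is to "Record nodule characteristics, including location in the lobe, distance from pleura" and related features. The synopsis describes a single-arm, open-label registry and non-randomized data. Section 11.1 says that the study is observational, tests no formal hypothesis and had no formal sample size calculation.

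On analysis, the synopsis and section 11.1 give descriptive statistics, optional subgroup summaries, and 95% confidence intervals for key variables and for measures of effect and association that are not named. Section 11.2.1 defers the detail to a written SAP, which is not among the documents supplied.

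**The concern.** Read together, the two gap statements and the best-practice aim suggest that the registry will tell surgeons which localization technique works better. The design cannot do that unaided. Technique is the surgeon's choice. The operators are "Thoracic surgeons of varying levels of experience in EMN-guided percutaneous localization" at about five sites. Dye and other markers may be combined in one subject (synopsis study procedures; section 9.9). The synopsis itself lists nodule size, depth, location and solid or ground-glass type as determinants of success.

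The analysis text names nodule size among its example subgroups, but not technique, site or operator, and it describes no stratification or model. Its reference to treatment subgroups would allow a success-by-technique table with confidence intervals. The steering committee analyzes and reports data periodically, so such a table could reach surgeons with a site, operator or case-mix difference presented as a technique effect.

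**Working it through.** The plan gives no figure to reproduce: 70 to 100 subjects is stated without a formula, and no expected success rate is given. The check has two parts. Every rate, share and split below is an assumption.

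**What the plan commits to**

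| Topic | Aim or rationale | Commitment |
|---|---|---|
| Best practice | Identify, analyze, promulgate (synopsis, section 4); understand (section 3) | No objective or estimate defined for it |
| Technique | Evaluation and comparison named as the gap | Report or record only (4.3.1) |
| Success | – | One overall percentage (4.1, 9.2) |
| Inference | – | Descriptive; no hypothesis (synopsis, 11.1) |

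No row contains a technique contrast, so no scheduled estimate is exposed to confounding by technique. The overall percentage can be estimated whatever the technique mix. At an observed 90%, the exact 95% interval is 80.5 to 95.9% with n = 70 and 82.4 to 95.1% with n = 100.

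**What an unplanned crude table could show**

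1. *Case mix, no technique effect.* Let success be s_E in easier and s_H in harder nodules, and let the share of harder nodules be h_A and h_B under two techniques. The crude gap is (h_B − h_A) × (s_E − s_H).
   - Middle case: (0.70 − 0.30) × (0.95 − 0.80) = 0.06, or 6 points (90.5% against 84.5%).
   - Low end: (0.60 − 0.40) × (0.95 − 0.85) = 0.02, or 2 points.
   - High end: (0.80 − 0.20) × (0.95 − 0.75) = 0.12, or 12 points.
   - Equal shares: 0. More extreme assumptions give more: (0.80 − 0.10) × (0.95 − 0.65) = 0.21.

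2. *Precision with no confounding.* For two groups of n each, both with observed success p and Wilson limits l and u, the Newcombe 95% half-width is √[(p − l)² + (u − p)²].
   - n = 35, p = 0.85: l = 0.698, u = 0.933; √(0.152² + 0.083²) = 0.173.
   - n = 35, p = 0.90: 0.155.
   - n = 50, p = 0.85: 0.144.
   - n = 50, p = 0.90: l = 0.786, u = 0.957; √(0.114² + 0.057²) = 0.127.
   - An 80/20 split of 70 to 100 subjects gives full widths of 32 to 42 points.

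3. *Room for adjustment.* Five sites give 70/5 = 14 to 100/5 = 20 subjects each. Expected failures per site are 14 × 0.10 = 1.4 to 20 × 0.15 = 3.0. At the six-subject site minimum they are 6 × 0.10 = 0.6 to 6 × 0.15 = 0.9.

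4. *Identifiability.* If each of five sites used a single technique, five site indicators plus a technique indicator would have six columns but rank 5. No model could then separate technique from site. If techniques vary within sites, the rank is 6 and the effect is estimable, subject to the sparse failures in step 3.

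A confounded gap is therefore possible in an unplanned table. In the 2-to-12-point range it would be smaller than the ±12.7 to ±17.3 points of sampling uncertainty. With one to three failures per site, stratified or modelled contrasts would be wide or impossible.

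**The case for a change.** The strongest case for a change is that the mismatch is in current text: the objectives are descriptive, yet the aim is to send evidence-based best practice to surgeons. The protocol names the likely confounders itself, collects the nodule features and the technique, and could add a limiting sentence and a few tables cheaply. A later SAP would not alter the aims as worded in the synopsis and sections 3 and 4.

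Part of this stands. To the extent that best practice means one technique against another, the aim outruns a single-arm registry with surgeon-chosen technique, and a success-by-technique table should not be read as comparative evidence.

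The step from wording to defect does not stand. In the synopsis, best practice refers to intraoperative percutaneous localization as a whole. After naming the gap, the synopsis commits only to collecting and recording techniques. Best practice can also mean procedural know-how, such as patient position, registration, and dye type and volume, all recorded under section 9.9. Harm needs three further steps: the table is produced, it is read causally, and it is promulgated without caveat. The extra site-by-nodule tables would be mostly sparse cells, and rules for a technique contrast would govern an analysis that nobody has scheduled. The surgeons also receive common training on the tools and techniques, which narrows operator differences without removing them.

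**Conclusion.** No change to the plan follows. The tension between the stated aim and the design is real but confined to wording. The primary percentage is unaffected, no technique contrast is planned in the supplied text, and the descriptive, non-randomized, hypothesis-free nature of the study is already stated. Analysts working from that text have what they need: any breakdown by technique is descriptive, is best read beside site and nodule features, and supports no comparative conclusion.

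The size of any distortion cannot be derived from the documents. The 2-to-12-point range rests wholly on assumed success rates and nodule mixes, and is zero for case mix if that mix is equal across techniques. The ±13 to ±17 points for an unconfounded contrast assumes 85 to 90% success and equal groups. The conclusion is limited to the supplied text, because the SAP promised in section 11.2.1 was not available and may treat technique further. It would change if a success-by-technique comparison were made a formal objective.
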